10.2 Secondary Efficacy Analyses

There will be one secondary per-protocol efficacy analysis comparing all intervention and control subjects who received the assigned intervention for at least 3 months. The per-protocol analysis will be identical to the intention to treat analysis, except for the number of subjects included. For further clarity, it will consist of analyses of the same primary endpoint and five secondary endpoints, but only subjects that received the assigned intervention for 3 months will be included in comparisons. Because some patients may stop methotrexate due to intolerance before 3 months it was decided to conduct a modified per protocol analysis. The modified per-protocol analysis will include all patients receiving study medications for at least 3 months and all patients stopping medications before 3 months due to intolerance or toxicity. Physicians and parents are asked to report in separate case report forms if the patient is receiving ondansetron. If information is missing from one source, the other source will be considered true. If information is missing from both sources, the site investigator will be asked to verify ondansetron status against their clinical records.

11 Safety Analyses

OPT-JIA will assess the safety and tolerability of premedication with ondansetron, compared to as needed use. The safety endpoints are the frequency and cumulative incidence of adverse events and any serious unexpected suspected adverse drug reactions (SUSARs). Safety parameters in the OPT-JIA trial will be assessed using the standard set of questions about adverse events that are part of the CAPRI JIA Registry. These questions will be asked from the attending physician every time the study participant attends the pediatric rheumatology clinic for a medical visit. The form lists the following adverse events: abdominal pain, nausea/vomiting, rash (not JIA rash), injection reaction, infusion reaction, gastrointestinal bleed, abnormal blood counts, abnormal liver function tests, anaphylaxis, infection with hospitalization, tuberculosis, opportunistic infection, demyelinating disease, inflammatory bowel disease, malignancy, gastrointestinal perforation, eye surgery, joint surgery, and macrophage activation. Any non-listed events are reported as "Other / Not listed" by entering a description of the adverse event.

Frequency and cumulative incidence of adverse events: At every visit to the pediatric rheumatology clinic the rheumatologist is asked if an actionable adverse event has occurred since the previous visit (ADVERSE_EVENT = 1 if Yes, ADVERSE_EVENT = 0 if No). The physician then chooses the type of adverse event from the list of possible adverse events or enters the nature of the event if not listed. For each event, the physician reports what was done to address the event (additional visits, additional treatments, additional tests, hospitalization, surgery or change in anti-rheumatic medications). For each event, the physician reports if the event was serious. Actionable adverse event is defined as any untoward medical occurrence in a patient in the registry that requires additional medical visits, investigations, treatments, or a change in arthritis medications, **irrespective of its cause.** A serious adverse event is one that results in death, is life-threatening, requires hospitalization (admission for overnight stay), or results on a significant disability or a congenital anomaly. Or an adverse event that requires medical or surgical intervention to prevent dead, significant disability or a congenital anomaly.

Additionally, site principal investigators report directly to Health Canada and the study sponsor ([name]) via fax any observed Serious Unexpected Suspected Adverse Drug Reactions (SUSARs) to Ondansetron within 24h of becoming aware of such occurrence, using the forms provided by Health Canada.

The final safety analysis will be conducted on the intention to treat population and consist of:

- A full listing of all the adverse events reported in the trial.
- A summary table comparing number and percentage of patients experiencing the most commonly reported adverse events in the intervention and control groups.
- The rates of adverse events for intervention and control groups calculated as number of events per 100 person-years of observation.
- The cumulative incidence of patients experiencing adverse events within 52 weeks in intervention and control groups, and 95% CI, calculated using Kaplan Meier survival methods.
- A figure showing the Kaplan Meier adverse event cumulative incidence curves for intervention and control groups within 52 weeks of enrolment.
- A comparison of the cumulative incidence curves for intervention and control groups using a log-rank test and reporting the corresponding p-value.

12 Other Analyses

In addition to estimates of intolerance-free survival and cumulative incidence of events, figures will show the corresponding Kaplan Meier curves from enrolment to 52 weeks with a table of subjects at risk in intervention and control groups at 10-week intervals underneath each figure.

13 Reporting Conventions

Medians and 25th, 75th centiles will be reported to one decimal place if applicable. Means and standard deviations for MISS scores and quality of life scores will be rounded to one decimal place. Time will be reported in full weeks throughout. Percentages will be rounded to 1 decimal place. P values will be reported to 3 decimal places. Any p values smaller than 0.001, will be reported as p<0.001. Kaplan Meier estimates of the probability of survival and cumulative incidence of events of interest will be reported as percentages with one decimal place.

14 Quality Assurance of Statistical Programming

The OPT-JIA interim and final statistical analyses will be conducted by the PhD student [name] and the results and statistical code will be verified by [name].

All final statistical code and outputs will be filed in the OPT-JIA files at the BC Children's Hospital network computer servers.

Any outputs will have the

- date and time included
- the name of the code file that produced the analysis
- the author

At the start of any code file there will be a set of comments that give

- the author
- the date and time of writing
- references to inputs and outputs
- reference to any parent code file that runs the child code file

15 Summary of Changes to the Statistics

Changes to the statistical analysis outlined in the OPT-JIA protocol V3, September 2, 2019, concerned primarily the interim analysis (described in the following paragraphs). There were no changes to the 6-monthly safety analyses. The changes of note for the final efficacy analysis were the use of Kaplan Meier estimates to allow for patients with incomplete follow-up and calculate the risk ratio, and the use of a modified per protocol analysis that included participants who stopped medications before 3 months because of intolerance or toxicity.

With the agreement of the Steering Committee and the Data and Safety Committee, the interim analysis took place at an earlier stage than initially specified because of the slow enrolment into the study. The interim analysis was planned by [name] with the assistance of [name] and discussed with the PI, [name], in March 2023. It was discussed and approved at the steering committee call of April 21, and at the Data and Safety Committee call on May 8, 2023, and further confirmed with the DSC chair via email on October 5, 2023. The approved plan was to extract information from the REDCap database on September 30, and this was postponed to October 6, to allow time for responses to remaining queries to be verified by site principal investigators. The sample sizes for the interim analysis were smaller than had been expected, and hence there were only 27 patients on whom success or failure had been definitively determined at the time the interim analysis was conducted with data extracted on October 6th, 2023. There were an additional 17 participants who were still on the trial, with at least one follow-up visit but not yet to their 52-week visit. We therefore used the Kaplan-Meier (KM) statistical analysis technique separately in each group to estimate the probability of success in each group in a way that would make some use of the partial information provided by the patients with incomplete follow-up periods.

We used the KM method to estimate the probability of success at 52 weeks and formed the relative risk (RR) by dividing the estimated probability for the intervention group by the estimated probability for the control group. The statistical properties of the RR are better expressed on the log scale, so we computed the log of this ratio, which is equivalent to the difference between the two logged survival probabilities. We computed the standard error for this difference using the separate standard errors for each logged survival probability and computed the confidence interval on this log scale using the standard normal (Wald) method. The same KM methods will be applied for the final efficacy analysis.

According to the O'Brien-Fleming alpha-spending rule [17], we used alpha=0.0045 for the interim analysis rather than 0.05 so that we would maintain maximum power in the final analysis while controlling the probability of falsely discovering a difference between the two treatments if there is none. Once the confidence interval was computed on the log scale, we exponentiated the two endpoints to transform it into the original relative-risk scale. These are standard techniques described, for example, in books on survival analysis [20].

References

7. Ontario Drug Benefit Formulary <https://www.formulary.health.gov.on.ca/formulary/>. Accessed February 2018.

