4.1 Preface

Methotrexate is the most widely used disease-modifying anti-rheumatic drug (DMARD) for the treatment of children with Juvenile Idiopathic Arthritis (JIA). In children, methotrexate side effects such as nausea, vomiting and abdominal discomfort can lead to conditioned methotrexate intolerance with anticipatory nausea/vomiting and avoidance behaviours (in up to 50% of children). Methotrexate intolerance leads to poor adherence to optimal dosing or to stopping the medication altogether. Children who cannot adhere to optimal dosing or stop methotrexate may require expensive biologic medications to control their JIA.

The Ondansetron Premedication Trial in Juvenile Idiopathic Arthritis (OPT-JIA) is a registry-based pragmatic adaptive superiority randomized clinical trial to evaluate if routine premedication with the anti-emetic ondansetron reduces methotrexate intolerance and increases the proportion of children with JIA able to continue taking methotrexate, resulting in a better quality of life and more cost-effective medication use. OPT-JIA is a Health Canada regulated trial that adheres to the International Council for Harmonization of Technical Requirements for Pharmaceuticals for Human Use (ICH) guidelines for design, analysis and reporting.

All OPT-JIA data is collected via the Canadian Alliance of Pediatric Rheumatology Investigators (CAPRI) JIA Registry. The CAPRI Registry captures information on clinical characteristics, outcomes and adverse events of children with JIA across all Canadian pediatric rheumatology centres, at every visit to clinic. The Registry started in 2017, and as of October 2023, it contains information on >1200 children. OPT-JIA does not have fixed time intervals for data collection. Data is collected for one year after study enrolment at clinic visits that are scheduled according to patient needs.

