5.1 Study Objectives

(ICH E3; 8.)

The aim of OPT-JIA is to determine the effectiveness of prophylactic use of ondansetron in patients with JIA starting methotrexate in Canadian pediatric rheumatology practices (intervention), compared to as-needed use in those children who develop nausea/vomiting (control).

Specific Objectives:

To compare:

- 1) The proportions of patients remaining on methotrexate with no intolerance between the two groups one year after starting methotrexate (primary endpoint).
- 2) The safety and tolerability of premedication with ondansetron, compared to as needed use.
- 3) The 1-year cumulative incidence of: a) methotrexate intolerance, b) attainment of inactive disease, c) biologic medication initiation
- 4) The mean quality of life scores and methotrexate intolerance severity scores between the two groups 4-8 months after starting methotrexate.

OPT-JIA also collects information on impacts on quality of life (to calculate health utilities) and medication utilization that will enable a future cost-effectiveness analysis.

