Our primary outcome statistic is the ratio of two proportions (relative risk, RR): the proportion of randomized children remaining on methotrexate with no intolerance one year after enrolment in the intervention group divided by the same in the control group. Subjects stopping ondansetron or methotrexate for toxicity or lack of efficacy will be counted as trial failures in calculations for the primary endpoint, irrespective of their MISS scores. A 95% CI for the RR will be calculated and the null hypothesis will be rejected if the confidence interval is entirely above 1. Considering that an interim analysis will be conducted, the alpha used in the final analysis will be 0.05 minus the alpha used in the interim analysis. As stated above, due to patient withdrawals and the fact that OPT-JIA did not have fixed-date visits, a number of patients was expected not to have a documented primary endpoint within the 52-week window, and a decision was made to use instead the Kaplan Meier estimates of the probability of success for calculations of the relative risk.

Cumulative incidence of methotrexate intolerance within one year: The Kaplan Meier survival analysis estimate of the cumulative incidence of a MISS score of 6 or more points within 52 weeks of study enrollment, as defined above. Kaplan-Meier curves will be constructed separately for intervention and control groups and the curves will be compared using the log-rank test.

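### A non-serious ondansetron reaction managed only by stopping or reducing ondansetron enters no planned adverse-event summary, although ondansetron tolerability is a trial objective

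*SAP*

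**What the plan says.** Section 5.1 makes this the second objective: "The safety and tolerability of premedication with ondansetron, compared to as needed use". Section 11 repeats it as the purpose of the safety analysis.

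Section 11 takes its safety data from the registry's standard questions. At each visit "the rheumatologist is asked if an actionable adverse event has occurred since the previous visit", and the answer is coded yes or no. An event is actionable, whatever its cause, if it is "any untoward medical occurrence in a patient in the registry that requires additional medical visits, investigations, treatments, or a change in arthritis medications". For each reported event the physician then records what was done, from this set: "additional visits, additional treatments, additional tests, hospitalization, surgery or change in anti-rheumatic medications". Neither the definition nor the action set mentions ondansetron.

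Section 4.1 states the trial question as whether "routine premedication with the anti-emetic ondansetron reduces methotrexate intolerance", which places the drug outside the arthritis and anti-rheumatic medications.

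Section 10.1 handles stops of the study drug under efficacy: "Subjects stopping ondansetron or methotrexate for toxicity or lack of efficacy will be counted as trial failures".

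**The concern.** The event definition was written for a registry of arthritis treatment and is used here for a trial of an anti-emetic. A change in an arthritis drug is enough to make an event count, but a change in the drug under test is not. Stopping a drug because of a reaction to it is a direct sign of poor tolerability, and tolerability is what objective 2 asks about.

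The two arms are not equally exposed to the omission. Under section 6.1 every intervention child is prescribed weekly ondansetron, whereas controls receive it only if they report nausea or vomiting and the rheumatologist chooses to prescribe it. Uncounted ondansetron reactions would therefore be expected to fall more often in the intervention arm. The between-arm comparison of adverse events would then lean towards premedication looking better tolerated.

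**Working it through.** No arithmetic applies: the SAP states no rate of ondansetron reactions and no figure that could be reproduced. The check is to follow one case through the text.

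**Case.** A child has a non-serious reaction to ondansetron. At a routine visit the drug is stopped or reduced. There is no extra visit, test or treatment, and methotrexate and other arthritis drugs are unchanged.

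| Provision | Where | Does it capture the case? |
|---|---|---|
| Additional visits, investigations or treatments | Section 11 definition | No; none took place |
| Change in arthritis medications | Section 11 definition | No; ondansetron is an anti-emetic (section 4.1) |
| Any-cause wording | Section 11 definition | No; it widens the admissible causes, not the qualifying actions |
| Free-text entry for unlisted events | Section 11 | No; event type is entered after the actionable question has been answered yes |
| Serious adverse event | Section 11 | No; the case is non-serious |
| SUSAR reporting | Section 11 | No; it requires a serious and unexpected reaction |
| Safety rows of the assessment schedule | Section 6.4 | No; the rows are actionable events, serious events and SUSARs |

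A site applying the definition codes the visit as having no adverse event. Every output in the section 11 list is built from reported events, so the child is missing from the full listing, the summary table, the rate per 100 person-years, the Kaplan-Meier cumulative incidence and figure, and the log-rank test. No table in section 16 is described as reporting ondansetron discontinuations.

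**Where the case can still appear.**

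1. Section 10.1 makes a stop of ondansetron for toxicity a primary-endpoint failure. This is an efficacy count. It is pooled with stops for lack of efficacy and with stops of methotrexate, and it does not cover a reduction.
2. Section 10.2 keeps children who stop medications before 3 months because of intolerance or toxicity in the modified per-protocol set. This governs membership of an analysis set and is not a safety count.

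**The first route is not secure.** Section 8.5.3 defines failure for the Kaplan-Meier endpoint as stopping methotrexate or experiencing intolerance. Section 10.1 also describes the endpoint as having those two components, and then adds ondansetron stops. Section 15 says the same Kaplan-Meier methods apply to the final analysis. The SAP therefore does not settle whether a child who stops ondansetron for toxicity but continues methotrexate without intolerance is a failure.

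**The case against.** The strongest reply is that the gap is narrow. The definition applies whatever the cause, so any ondansetron reaction that leads to an extra visit, test or treatment is counted, even if ondansetron is also stopped. Serious unexpected reactions have their own reporting route. The endpoint is secondary, and the omission itself changes no alpha level or stopping rule. The protocol is not at hand, and the case report forms that section 10.1 says are appended are not shown either; they may record a reason for stopping. All of this stands. It limits the size of the problem but does not change what the SAP's own definition excludes.

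Three stronger readings are tempting and are not supported:

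- A reader might infer that such a reaction is never counted as harm at all. Section 10.1 does count an ondansetron stop for toxicity against the child's arm in the primary endpoint. The accurate statement is that the reaction enters no adverse-event summary.
- A reader might infer that the prompted event list is blind to ondansetron. It includes abdominal pain, nausea/vomiting, rash and anaphylaxis. A suspected QT or serotonin event, both named as risks in the exclusion criteria of section 6.2, would very likely need a test or treatment and could then be entered as free text.
- A reader might infer a further imbalance because starting ondansetron for nausea in a control child could be read as an additional treatment, and so as an adverse event. The SAP does not say whether sites read it that way.

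**Conclusion.** The point holds as a gap in the safety reporting. A non-serious reaction handled only by stopping or reducing ondansetron falls outside the adverse-event definition and all the outputs built on it, while the tolerability of ondansetron is objective 2. A stop may show up as an efficacy failure or as a reason for per-protocol inclusion. Neither reports tolerability, and the first depends on an unresolved conflict between sections 8.5.3 and 10.1.

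The expected direction favours premedication. This rests on one assumption: that reactions of this kind are about as likely per exposed child in either arm, with fewer controls exposed. The size cannot be computed from the SAP and may be small, so the documents do not support a claim that the adverse-event comparison is materially biased. The conclusion also assumes that sites apply the written definition literally and that no form outside the SAP feeds such events into the safety tables.

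**What to change.** 1. Add to Table 6 a descriptive row, by arm, for children who stopped or reduced ondansetron because of an adverse reaction. Start from the toxicity stops that section 10.1 already requires to be identified, and ask sites to confirm the reason where it is unclear. Reductions will need such confirmation, because section 10.1 covers stops only.
2. Do not derive these events from the ondansetron use and dose field alone. Section 6.4 does not show that it carries a reason, and under section 6.2 ondansetron also ends when methotrexate ends.
3. For visits from now on, add a change in or stop of ondansetron to both the qualifying actions and the recorded actions. Flag events that qualify only by this route. The rates, Kaplan-Meier curve and log-rank test can then still be run on the existing registry definition across the whole trial, without mixing two capture rules in one comparison.
4. Reconcile sections 8.5.3 and 10.1 on whether stopping ondansetron for toxicity is a primary-endpoint failure, and state the answer once.

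The cost is some SAP wording, one added option on the form, a few site queries, and adverse-event counts that may be slightly higher when the flagged events are included.

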6.3 Randomization and Blinding

(ICH E3; 9.4.3, 9.4.6. ICH E9; 2.3.1, 2.3.2)

Patients are assigned 1:1 online after confirming eligibility, using the Registry and block randomization by Canadian region and patient weight to one of two groups:

Intervention	routine premedication with oral ondansetron (2 mg if <15Kg, 4 mg if 15-30Kg, 8 mg if >30Kg; 3 doses a week)
Control	oral ondansetron at the same dosing, prescribed only to those who develop methotrexate-induced nausea/vomiting during usual care.

There is no blinding (masking) of treatment assignment.

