6.4 Study Assessments

(ICH E3; 9.5.1. ICH E9; 2.2.2)

Visit	Baseline	Every Visit	Visit Month 12
History and examination	x	x	x
QOL questionnaire	x	x (\pm 14)	x (\pm 14)
MISS	x	x (\pm 14)	x (\pm 14)
Actionable AEs	x	x	x
SAEs	x	x	x
SUSARs	x	x	x
Concomitant medication	x	x	x
Methotrexate use and dose	x	x	x
Ondansetron use and dose	x	x	x

Analysis Time Windows

Visit (target day)	Lower bound (days)	Upper bound (days)
Baseline (0)	N/A	N/A
Every visit to clinic (time window not applicable)	N/A	N/A
Month 4-8 (180)	120	240
Month 12 (364)	308	420

7 Sample Size

(ICH E3; 9.7.2. ICH E9; 3.5)

Our primary outcome statistic is the ratio of two proportions (relative risk, RR): the proportion of randomized children remaining on methotrexate with no intolerance in the intervention group divided by the same in the control group. Our sample size calculation is based on expressing the RR in the log scale and using established formulas for standard errors [15, 16]. With $p<0.05$, power of 90% and expected methotrexate continuation with no intolerance of 50% in the control group and 75% in the intervention group the result is 79 evaluable subjects per group. We will aim to recruit 176 subjects total to allow for up to a 10% dropout rate.

8 General Analysis Considerations

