8.5.9 Documentation of Interim Analyses

All interim analysis data files, preliminary statistical output and final interim analysis report for the DSC will be preserved in the OPT-JIA Trial folders at the institutional computer servers controlled by the BC Children's Hospital in Vancouver, under the custody of [name]. Copies of all email communications pertaining the interim analysis between the study biostatisticians, study PI and the chair of the DSC will also be preserved in these folders.

9 Summary of Study Data

All variables will be summarized separately for subjects assigned to the intervention and to the control group and shown in side-by-side columns in tables in that order. Descriptive categorical variables at baseline will be summarized as frequencies and percentages. Descriptive continuous variables at baseline will be summarized as medians and 25th and 75th centiles. Efficacy categorical variables will be summarized as frequency and percentages. Efficacy continuous variables (MISS scores and quality of life scores) will be summarized as means and standard deviations.

Between-groups comparisons of baseline characteristics will be made using Fisher exact tests for categorical variables and the Wilcoxon rank sum test for continuous variables, and the corresponding p value reported. All tests will be double sided and p values <0.05 will be considered statistically significant.

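### Section 11 compares adverse events between arms by a log-rank p-value and names no between-arm difference or ratio with a confidence interval

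*SAP*

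**What the plan says.** SAP section 5.1 makes safety a comparative objective: "The safety and tolerability of premedication with ondansetron, compared to as needed use".

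SAP section 11 gives a closed list of six items for the final safety analysis, on the intention-to-treat population:

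- a full listing of events;
- a table of the commonest events by arm, as numbers and percentages;
- event rates per 100 person-years by arm;
- 52-week cumulative incidence "in intervention and control groups, and 95% CI, calculated using Kaplan Meier survival methods";
- a figure of the curves;
- "A comparison of the cumulative incidence curves for intervention and control groups using a log-rank test and reporting the corresponding p-value".

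Section 9 sets the general reading rule: "All tests will be double sided and p values <0.05 will be considered statistically significant". That sentence closes a paragraph on baseline comparisons but is worded to cover every test.

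The primary efficacy endpoint is handled differently. Section 10.1 gives it a relative risk with a CI, and section 15 explains how to form that ratio from two Kaplan-Meier estimates. Section 7 sizes the trial on this endpoint alone.

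**The concern.** A comparative objective calls for an estimated comparison. In section 11 the estimates are by arm, and the one step that joins the arms is a p-value. A log-rank p-value gives neither the size of a difference nor the range of differences compatible with the data. Two arm-specific CIs do not display that range either, because the interval for a difference cannot be read from whether they overlap.

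Premedication gives ondansetron to every child in the intervention arm, while the control arm receives it only when symptoms appear. The safety contrast is therefore part of the case for or against routine use. If the trial is too small to detect a relevant rise in adverse events, a non-significant test sits beside objective 2 with no statement of the excess that has not been ruled out.

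**Working it through.** **Inputs from the SAP.** Two-sided 0.05 (section 9). 1:1 allocation: "Patients are assigned 1:1 online after confirming eligibility" (section 6.3). Sizing basis: "power of 90% and expected methotrexate continuation with no intolerance of 50% in the control group and 75% in the intervention group", for which "the result is 79 evaluable subjects per group" (section 7). Recruitment: "We will aim to recruit 176 subjects total to allow for up to a 10% dropout rate", that is 88 per arm. Safety horizon: 52 weeks (section 11).

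**Input the SAP does not give.** The 52-week adverse-event risk in the control arm. I assume 10% to 70% and show the range.

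**The plan's own figure.** On the log relative-risk scale, with pooled variance under the null and mean proportion 0.625:

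n = [1.960·√(2·0.375/0.625) + 1.282·√(0.5/0.5 + 0.25/0.75)]² / (ln 1.5)²
= [1.960·1.0954 + 1.282·1.1547]² / 0.1644 ≈ 80 per group.

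This is within one of the stated 79. Exact binomial power of the Wald log-RR test at 79 per group is 90.3%. For dropout, 158/0.9 = 175.6, so 176. The sizing is reproduced. It contains no safety term.

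**Chance that the log-rank test misses a rise.** Schoenfeld's formula with exponential times and no dropout:

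- HR = ln(1 − pT)/ln(1 − pC)
- expected events D = n(pC + pT)
- power = Φ(ln HR·√D/2 − 1.96)

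Example, 20% vs 30% at 88 per arm: HR = 0.3567/0.2231 = 1.598, ln HR = 0.469, D = 44. Power = Φ(0.469·6.633/2 − 1.96) = Φ(−0.40) = 34%, so the miss rate is 66%.

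| Control risk | 10-point rise missed, n = 79 / 88 | 15-point rise missed, n = 79 / 88 |
|---|---|---|
| 10% | 55% / 51% | 25% / 20% |
| 20% | 69% / 66% | 42% / 37% |
| 30% | 73% / 71% | 49% / 44% |
| 40% | 75% / 73% | 51% / 47% |
| 50% | 74% / 72% | 49% / 45% |
| 70% | 65% / 62% | 29% / 24% |

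A simulated log-rank test (4,000 replicates per cell, control risks of 10% to 50%) agrees within about 5 points.

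**What an interval would show.** For equal risks p, the half-width of a 95% CI on the difference is about 1.96·√(2p(1 − p)/n).

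| Risk | n = 79 | n = 88 |
|---|---|---|
| 20% | ±12.5 points | ±11.8 points |
| 30% | ±14.3 points | ±13.5 points |
| 40% | ±15.3 points | ±14.5 points |
| 50% | ±15.6 points | ±14.8 points |

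So at planned size a near-zero observed difference would still be compatible with an excess of roughly 12 to 16 points. The p-value alone does not tell the reader that.

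**The case against.** **The plan is not a p-value alone.** It also gives counts, rates and Kaplan-Meier incidences with CIs by arm. The arms are independent, so a reader could combine the two standard errors into an approximate interval for the difference. This stands. The gap is that no contrast is prespecified in section 11, not that the data for one would be missing.

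**Table 6 may contain a contrast.** Section 16 plans a Table 6 comparing adverse events by arm, and its shell was not in the text available for review. The Table 4 shell has a relative-risk column with a CI, so Table 6 may have one too. A reader might infer that no effect estimate is planned anywhere; that cannot be shown. What can be said is that the text of section 11 names none.

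**No margin is needed.** A reader might call the lack of a safety margin an error. The SAP states no non-inferiority hypothesis for safety, so it is not.

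**No claim of equivalence is made.** A reader might infer that p ≥ 0.05 will be taken to mean equal safety. The SAP does not say so and ties no safety decision to the test.

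**Low safety power is common in trials sized for efficacy.** True, and it is not in itself a fault here. It is why an interval is more useful than a test. Nor can one miss rate be quoted: a 15-point rise would be missed only about 20% to 29% of the time at control risks of 10% or 70%.

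**The trial may end smaller.** Section 15 reports 27 children with a determined outcome and 17 still in follow-up at the interim. It is tempting to treat those 44 as the final size. Section 8.1 brings every enrolled child into the final analysis, so the interim count does not predict it.

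**An any-event contrast can mislead.** Section 11 counts actionable events whatever their cause, and the form lists nausea/vomiting and abdominal pain, which premedication may reduce. Fewer of these could hide an excess of other harms. This stands and shapes the fix.

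**Conclusion.** The point holds as a matter of analysis choice. Section 11 answers a comparative objective with arm-level estimates and one log-rank p-value, and its text specifies no between-arm difference or ratio with a CI.

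The size of the problem depends on a control-arm risk that the SAP does not give. Over assumed risks of 10% to 70%, the test misses a 10-point rise more often than not. For a 15-point rise the result runs from adequate power to about a coin toss. These figures assume exponential event times and no dropout; the 79 to 88 range brackets the evaluable and recruited numbers. They support the statement that a non-significant result would be weakly informative. They do not show that premedication is harmful, or that a non-significant result is the likely outcome whatever the true effect.

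**What to change.** In section 11, and in Table 6 if it has no such column:

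1. Make the main safety comparison the intervention-minus-control difference in 52-week Kaplan-Meier adverse-event incidence with a two-sided 95% CI, its variance being the sum of the two arm variances.
2. Add the ratio of event rates per 100 person-years with a 95% CI that allows for repeat events in the same child, for example by a variance clustered on the child.
3. Report both for any event, and again for events excluding nausea/vomiting and abdominal pain.
4. Keep the log-rank p-value as descriptive, and state that p ≥ 0.05 will not be reported as evidence of similar safety.

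The cost is a few lines of SAP text and slightly more analysis of data already collected. No extra children or visits are needed. The one drawback is that the safety statement will look less certain, which reflects what a trial of this size can show.
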